5.3.3. Additional Efficacy Outcomes

5.3.3.1. All-cause Mortality through Day 30 and Follow-up

The number and percentage of subjects who died up through the FU visit (all-cause mortality) will be summarized by treatment group in the ITT and mITT populations. The 25th, 50th (median), and 75th percentiles will be provided by treatment group using Kaplan-Meier methods. Subjects who do not die or who are lost to follow-up will be censored at the last date known to be alive. The number and percentage of subjects censored will be provided. The Kaplan-Meier estimate of 30-day all-cause mortality will also be provided along with the 95% CI calculated using Greenwoods formula. The Kaplan-Meier curve will be presented by treatment group. A listing of the primary cause of death will also be provided.

5.3.3.2. Time to Negative Blood Culture

The time to negative blood culture (hours) will be analyzed using Kaplan-Meier methodology by treatment group, and for the CD101 treatment groups combined, in the mITT population. Summaries will include the 25th, 50th (median), and 75th percentiles. The number and percentage of subjects censored and the reason for censoring (receipt of more than 1 dose of non-study antifungal for the treatment of candidemia and/or IC [with the exception of a rescue antifungal],

CONFIDENTIAL Page 41 of 56

lost to follow up prior to having 2 negative blood cultures) will also be provided. A graph of the Kaplan-Meier curves will be provided.

5.3.3.3. Overall Success at Day 14 (± 1) by Baseline *Candida* species

The number and percentage of subjects programmatically determined to be an overall success (mycological eradication and resolution of clinical signs of candidemia) at Day 14 (± 1) will be summarized by baseline *Candida* spp. and treatment group for subjects in the mITT population.

Overall success by baseline *Candida* species and MIC cutoff for CD101, caspofungin and fluconazole at Day 14 (± 1) will be summarized by treatment group for subjects in the mITT population.

5.3.3.4. Mycological Success at Day 14 (±1) by Baseline *Candida* species

The number and percentage of subjects determined to be a mycological success (eradication/presumed eradication) at Day 14 (± 1) will be summarized by baseline *Candida* species and treatment group for subjects in the mITT population.

Mycological success by baseline *Candida* species and MIC cutoff for CD101, caspofungin and fluconazole at Day 14 (±1) will be summarized by treatment group for subjects in the mITT population.

5.3.3.5. Investigator's Assessment of Clinical Cure by Baseline *Candida* species

The number and percentage of subjects determined to be a clinical cure at Day 14 (±1) will be summarized by baseline *Candida* species and treatment group for subjects in the mITT population. The Investigator's assessment of clinical cure by baseline *Candida* species and MIC cutoff for CD101, caspofungin and fluconazole at Day 14 (±1) will be summarized by treatment group for subjects in the mITT population.

5.3.3.6. Exploratory Overall Response at Day 14 (±1) and Exploratory Mycological Response at Day 14 (±1)

The number and percentage of subjects having overall success, failure, and indeterminate response at Day 14 (± 1) will be summarized by treatment group for subjects in the mITT population. Exact 2-sided 95% CIs for the percentage of subjects who achieve success in each treatment group will be determined using the Clopper-Pearson method.

The number and percentage of subjects programmatically determined as having a mycological success (eradication), failure, or with an indeterminate mycological response at Day 14 (±1) will be summarized by treatment group for subjects in the mITT population. Exact 2-sided 95% CIs for the percentage of subjects who achieve success in each treatment group will be determined using the Clopper-Pearson method.

5.3.3.7. Exploratory Overall Success at Day 14 (± 1) by Baseline *Candida* species

The number and percentage of subjects with an exploratory overall success at Day 14 will be summarized by baseline *Candida* species and treatment group for subjects in the mITT population for Parts A and B combined. Exact 2-sided 95% CIs for the percentage of subjects who achieve success in each treatment group will be determined using the Clopper-Pearson method.

CONFIDENTIAL Page 42 of 56

5.3.3.8. Exploratory Mycological Success at Day 14 (±1) by Baseline *Candida* species

The number and percentage of subjects programmatically determined as having an exploratory mycological response at Day 14 (±1) of success (eradication) will be summarized by baseline *Candida* species and treatment group for subjects in the mITT population for Parts A and B combined. Exact 2-sided 95% CIs for the percentage of subjects who achieve success in each treatment group will be determined using the Clopper-Pearson method.

5.3.4. CD101 Plasma Concentration

Summary statistics (number of subjects, mean, SD, coefficient of variability % (CV%), median, min, max, geometric mean) of CD101 plasma concentration will be provided by time point and dose group for CD101 treated subjects in the PK population. Each CD101 dose group will be summarized separately for all timepoints and combined for all timepoints except Day 15. Only samples collected on Day1, Day 2, Day 4, Day 8 and Day 15 and within 10% of the nominal time (where applicable) will be included. Analyses of CD101 plasma concentration will only be conducted for Part A.

5.4. Analysis of Safety Data

All safety analyses will be conducted in the Safety population. Subjects who receive the wrong study drug for their entire course of treatment will be analyzed in the treatment group based on the drug received. All safety analyses will be completed for Part A, Part B, and for combined Parts A and B.

5.4.1. Adverse Events

Verbatim descriptions of AEs will be coded using MedDRA Version 19.0. Summary tables will be provided for all treatment-emergent adverse events (TEAE). A TEAE is defined as an AE that occurs during or after the administration of the first dose of study drug and up through the FU visit. An AE is programmatically defined as treatment emergent if the start date and time is on or after the start date and time of the first dose of study drug. If the time of an AE is missing, it is considered treatment emergent if it starts on the same date as the first dose of study drug. If AE start and end dates are missing entirely the event will be considered treatment-emergent.

An overall summary of TEAEs will include the number and percentage of subjects in each treatment group who experienced at least 1 TEAE in the following categories: any TEAE, any study drug-related TEAE, any severe TEAE, any serious TEAE (SAE), any study drug-related SAE, any SAE leading to death, and any TEAE leading to discontinuation of study drug. Subjects with multiple events will be counted only once within each category. Severity and relationship will be counted using the maximum severity and the strongest relationship respectively for a subject with multiple TEAEs.

The number and percentage of subjects reporting a TEAE in each treatment group will be tabulated by SOC and PT; by SOC, PT, and maximum severity (mild, moderate, or severe); and by SOC, PT, and relationship (unrelated or related) to study drug. The incidence of all TEAEs and all non-serious TEAEs that occur in at least 5% of subjects in the combined CD101 treatment groups will be summarized separately by PT and treatment group, sorted by decreasing frequency in the combined CD101 treatment groups. For all analyses of TEAEs, if the same TEAE (based on PT) is reported for the same subject more than once, the TEAE is counted only once for that PT and at the highest severity and strongest relationship to study drug.

CONFIDENTIAL Page 43 of 56

The number and percentage of subjects in each treatment group reporting a SAE, reporting a study drug-related SAE, reporting a TEAE leading to discontinuation of study drug will be summarized by SOC and PT.

The TEAE and maximum severity TEAE summaries by treatment group will also be presented for the Safety population in the hepatic insufficiency, renal function status, and renal disease subgroups defined in Section 3.8.

In addition to a listing of all reported AEs, by-subject listings of all SAEs (including any SAEs with an outcome of death) and all TEAEs leading to discontinuation of IV/oral study drug will be provided.

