1.2. Study Design

1.2.1. Synopsis of Study Design

This is a Phase 2, multicenter, prospective, randomized, double-blind study of CD101 IV or intravenous caspofungin followed by oral fluconazole step-down therapy for treatment of subjects with candidemia and/or IC. Subjects will be randomized at about 60 sites in North America (the United States [US] and Canada) and countries in Europe.

CONFIDENTIAL Page 9 of 56

In Part A, subjects will be randomized in a 1:1:1 ratio to receive CD101 IV treatment group 1, CD101 IV treatment group 2, or IV caspofungin using an interactive web response system (IWRS). Upon meeting specified criteria, oral step-down therapy is allowed in all 3 treatment groups: oral placebo in the CD101 IV groups and oral fluconazole in the IV caspofungin group. After approximately 90 subjects have been enrolled in the mITT population in Part A, enrollment into Part A of the study will close and Part B will begin. It is expected that approximately 114 subjects need to be randomized to achieve 90 subjects in the mITT population for Part A.

In Part B, subjects enrolled under Amendment 5 will be randomized in a 2:1 ratio until there are \geq 30 subjects in the CD101 IV treatment group 1 and \geq 15 subjects in the comparator group (\geq 45 additional subjects and no more than 120 subjects). Following the results of the unblinded analysis of Part A, the Part B subjects enrolled under Amendment 6 will be randomized in a 2:1 ratio to receive the CD101 IV treatment group 2 or IV Caspofungin. Total enrollment for Part B will depend on the enrollment rate for the period between the end of Part A and the start of the Phase 3 study, which is the trigger for Part B to stop enrollment. Oral step-down therapy is allowed in both treatment groups in Part B; oral placebo in the CD101 IV group and oral fluconazole in the caspofungin group. The total IV plus oral treatment duration will be \geq 14 days and up to a maximum of 21 days total for subjects with candidemia and up to a maximum of 28 days total for subjects with IC.

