3. GENERAL STATISTICAL METHODS

3.1. Sample Size Justification

This is an exploratory study and therefore, is not powered for inferential statistical analyses. A sufficient number of subjects are randomized to the CD101 IV and IV caspofungin treatment groups in Part A to provide an initial, substantive analysis of safety, tolerability, and estimate efficacy.

It is expected that approximately 114 subjects in Part A will need to be randomized given an estimated discontinuation rate of 20%, in order to achieve 90 evaluable subjects in the mITT population. In Part A, assuming a 73% overall success rate, the sample size of 30 subjects in the mITT population in each CD101 IV treatment group and the IV Caspofungin group will yield a 95% confidence interval (CI) for this success rate of 53.8% to 87.5%.

The addition of Part B in Amendment 5 of the protocol increased the study sample size by approximately 50% to 130% (depending on the rate of enrollment over the additional months to the staged start of the Phase 3 study and the rolling close-out of Part B). In Part B, subjects will be randomized until there are at least 30 subjects in the CD101 IV treatment groups at any dose and 30 subjects in the comparator group (≥45 additional subjects and no more than 120 subjects). In Part B, total enrollment will depend on the enrollment rate for the period between the end of Part A and the start of the Phase 3 study. With the addition of Part B subjects and assuming a 73% overall success rate, a total approximate sample size of 60 subjects in the CD101 treatment group (consisting of Group 1 from Amendment 5 and Group 2 from Amendment 6) will yield a 95% CI of 60.0% to 83.7%, and a total approximate sample size of 110 subjects in the CD101 treatment group (consisting of Group 1 from Amendment 5 and Group 2 from Amendment 6) will yield a 95% CI of 63.7% to 81.0%.

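### The two common-TEAE tables choose their rows on the combined CD101 rate alone, so they omit some terms common on caspofungin and tilt low-rate terms towards a CD101 excess (minor; one-line fix)

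*SAP*

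**What the plan says.** Section 5.4.1 of the SAP plans two frequency-restricted tables, one for all TEAEs and one for non-serious TEAEs. Each covers terms "that occur in at least 5% of subjects in the combined CD101 treatment groups will be summarized separately by PT and treatment group", with rows "sorted by decreasing frequency in the combined CD101 treatment groups". The columns are the treatment groups, but the row filter looks only at the pooled CD101 groups.

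The same section also plans tables with no frequency cut: "The number and percentage of subjects reporting a TEAE in each treatment group will be tabulated by SOC and PT", then again by maximum severity and by relationship to study drug. SAEs, drug-related SAEs and TEAEs leading to discontinuation have their own SOC/PT tables. Section 5.4.1 closes with listings: "In addition to a listing of all reported AEs, by-subject listings of all SAEs" and of TEAEs leading to discontinuation.

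Section 5.4 applies all of this to three datasets: "All safety analyses will be completed for Part A, Part B, and for combined Parts A and B".

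**The concern.** A table that sets treatment groups side by side should not choose its rows on the outcome in one of them. Doing so has three effects here.

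- **Comparator terms.** A term frequent on caspofungin and infrequent on CD101 does not appear in these two tables, however frequent it is on caspofungin.
- **Selection bias.** A term near the cut enters when its CD101 count happens to be high. The CD101 column is then inflated by selection and the caspofungin column is not, so equal true rates look like a CD101 excess.
- **Dilution across the two CD101 groups.** An event confined to one CD101 group is averaged with the other group before it meets the cut.

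The study is descriptive, so its tables are read at face value and no later test offsets a skewed row filter. At stake is a fair reading of two summary tables. The data themselves remain reported elsewhere.

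**Working it through.** **Inputs.** Part A is randomised equally to three groups (Section 1.2.1: "In Part A, subjects will be randomized in a 1:1:1 ratio to receive CD101 IV treatment group 1"). Section 3.1 expects about 114 randomised subjects to yield 90 in the mITT population at 20% discontinuation. Check: 90 / 0.80 = 112.5, so 113, or 114 as the next multiple of three. The plan's figure reproduces and gives 114 / 3 = 38 per group. I take 38 as the Safety population size, assuming that all randomised subjects are dosed. The lower bound is 30, from Section 3.1 ("the sample size of 30 subjects in the mITT population in each CD101 IV treatment group"). Event rates are assumptions.

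**Step 1: the cut in subjects.** With N CD101 subjects, a term needs t = 0.05N rounded up. At N = 76, 3.8 becomes 4 (5.3%). At N = 60, t = 3.

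**Step 2: terms common on caspofungin.** The probability of omission is P(X ≤ t − 1), with X ~ Binomial(N, CD101 rate). The caspofungin rate does not enter.

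- CD101 3%, N = 76: 0.099 + 0.232 + 0.269 + 0.205 = 0.81. At N = 60: 0.161 + 0.298 + 0.272 = 0.73.
- CD101 2%: 0.93 at N = 76 and 0.88 at N = 60. These hold whether caspofungin is at 10% or 20%.

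**Step 3: bias when all groups share a true rate p.** The expected CD101 rate among kept terms is E[X/N | X ≥ t]. The caspofungin expectation stays at p because that group is independent of the selection.

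| True rate p | Kept, N = 76 | CD101 rate if kept | Excess (points) | Kept, N = 60 | CD101 rate if kept | Excess (points) |
|---|---|---|---|---|---|---|
| 2% | 0.066 | 5.73% | +3.7 | 0.119 | 5.57% | +3.6 |
| 3% | 0.194 | 6.05% | +3.1 | 0.269 | 5.94% | +2.9 |
| 4% | 0.362 | 6.43% | +2.4 | 0.432 | 6.37% | +2.4 |
| 5% | 0.531 | 6.88% | +1.9 | 0.583 | 6.87% | +1.9 |
| 8% | 0.867 | 8.73% | +0.7 | 0.868 | 8.80% | +0.8 |
| 10% | 0.953 | 10.32% | +0.3 | 0.947 | 10.40% | +0.4 |

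**Step 4: a term on one CD101 group only (equal groups).** At 38 per group, 3/38 (7.9%) with 0/38 on the other is 3/76 and is omitted. A count of 4/38 (10.5%) with 0/38 is 4/76 and is kept. At 30 per group the largest omitted count is 2/30 (6.7%), and 3/30 (10%) is kept. With true rate q on one group and zero on the other, at 38 per group, the omission probability is 0.638 at q = 8%, 0.465 at 10%, 0.158 at 15% and 0.039 at 20%. In the pooled Parts A and B the split is not fixed. A group holding share s of CD101 subjects needs 5%/s on its own if the other has none.

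**Step 5: the remedy in Part A.** Select on 5% in any treatment group. This needs 2 subjects at 38 (1.9 rounded up) and at 30 (1.5 rounded up).

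- Equal true rates: the expected difference among kept terms is 0.0 points at every rate tried from 2% to 10%, by symmetry of equal groups.
- Caspofungin 10%, CD101 2%, 38 per group: P(0 or 1 event) is 0.0953 and 0.8240, so the term is kept with probability 1 − 0.0953 × 0.8240² = 0.94, against 0.07 now.
- Table length at a true 3% everywhere: 1 − 0.6837³ = 0.68 kept, against 0.19 now.

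**Step 6: the remedy in Part B.** Section 1.2.1 gives 2:1 randomisation with minimums of 30 and 15 under Amendment 5. I take one CD101 group of 30 against 15, with a true rate of 2% in both.

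| Rule | CD101 among kept | Caspofungin among kept | Difference (points) |
|---|---|---|---|
| Present (2 of 30 on CD101) | 7.36% | 2.00% | +5.4 |
| 5% in any group (2 of 30, or 1 of 15) | 3.36% | 5.71% | −2.3 |
| 5% and at least 2 subjects in any group | 6.11% | 4.45% | +1.7 |

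Without a minimum count, one caspofungin subject (0.05 × 15 = 0.75, rounded up to 1) brings a term in and the bias reverses.

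**The case against.** The strongest reply is that nothing goes unreported. Every TEAE appears by SOC, PT and treatment group without a cut, in three planned tables, and all AEs are listed. A reader might infer that caspofungin harms are hidden; the SAP does not support that, since the omission affects two tables only. The SAP also gives these two tables no special role. The interim set in Section 3.12 uses the table by SOC, PT and maximum severity, which has no cut, and Section 3.13 has the full Part A analysis use all summary tables.

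A reader might also infer that a signal on one CD101 dose is lost as a rule. It is not: with equal groups, any term observed in 10% or more on one dose is kept. Nor is there a large bias for truly common events, because the excess at a true 10% is 0.3 to 0.4 points. The distortion runs against the sponsor's own product, and the study makes no inference (Section 3.7).

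All of this stands and keeps the point minor. It does not justify filtering a between-group table on one side, and the uncut tables do not correct the two filtered ones.

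**Conclusion.** The point holds as a minor, cheap improvement. In Part A, a term at 10% on caspofungin and 3% on CD101 is left out of these two tables with probability 0.81 (76 CD101 subjects) or 0.73 (60). Kept terms with true rates of 2% to 5% carry a spurious CD101 excess of about 2 to 4 points, which fades to 0.3 to 0.4 points at 10%. Loss of a one-dose term in Part A is confined to observed rates under 10% on that dose. In the pooled set the limit depends on a split that the SAP does not fix. The figures assume independent binomial counts, 30 to 38 subjects per Part A group, and event rates chosen for illustration.

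**What to change.** In Section 5.4.1, change the row rule for both tables to: at least 5% of subjects, and at least 2 subjects, in any treatment group (either CD101 dose group or caspofungin). Keep the present sort by combined CD101 frequency.

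The cost is one line of SAP text, one programming condition and longer tables. The rule removes the equal-rate bias in Part A's equal groups. In Part B it reduces the bias without removing it, and the pooled groups need not be equal either. A footnote on both tables should state the selection rule and point to the uncut SOC/PT table.

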5.4.2. Clinical Laboratory Data

Several analyses of clinical laboratory data will be presented. For descriptive statistics of actual values and the change from baseline, values will be normalized against normal ranges from a common source (US National Library of Medicine [NLM], MedlinePlus) according to the following Scale Model formula (Karvanen):

$$s = x \frac{U_S}{U_X}$$

where s = the individual laboratory value normalized against the laboratory normal range from the common source; x = the original individual laboratory value; U_x is the upper limit of the normal range for an individual laboratory parameter; U_s is the upper limit of the laboratory normal range for that laboratory parameter from the common source.

Descriptive statistics (based on Systeme Internationale [SI] units) for chemistry, hematology and coagulation (baseline and unscheduled post-baseline only), and urinalysis (only pH and specific gravity) parameters as well as the change from baseline, will be summarized by treatment group for all study visits and for the worst overall post-baseline value. The directionality for determining the worst overall post-baseline value is provided in SAP Section 6.1. Change from baseline will be calculated for each subject at the specified time point as the value at the specified time point minus the baseline value.

The normalized laboratory values will be classified by toxicity grade according to the toxicity grading scales in SAP Section 6.2, which are based on the Division of Microbiology and Infectious Diseases (DMID) Adult Toxicity Scale, November 2007, the Division of AIDS (DAIDS) Table for Grading the Severity of Adult and Pediatric Adverse Events, December 2004, and the National Cancer Institute Common Terminology Criteria for Adverse Events (CTCAE, Version 4.0), Publish Date: 28 May 2009.

Shift tables will be presented to show the number of subjects with each toxicity grade at baseline versus each post-baseline visit and the worst post-baseline grade (including any unscheduled visits). For those laboratory parameters for which high toxicity grades are specified for both low and high values (eg, sodium, potassium), shifts in toxicity will be presented for high and low toxicities separately. The percentages will be based on the number of subjects with both a baseline and post-baseline (at the specified visit) assessment of the specific laboratory parameter. The number and percentage of subjects with at least a 2-grade increase from baseline at any post-baseline study visit, including unscheduled visits, will be summarized by laboratory

CONFIDENTIAL Page 44 of 56

parameter and treatment group. Percentages for each lab test will be based on the number of subjects with both a baseline and a post-baseline evaluation of the particular laboratory test. A listing will be provided which provides all results for a given laboratory test for subjects who have at least one 2-grade increase from baseline.

The number and percentage of subjects in each treatment group with an elevated transaminase level (>3 ×ULN, >5 ×ULN, and >10 ×ULN), an elevated total and direct bilirubin level (>1.5 ×ULN and >2 ×ULN) will be presented by study visit. A listing of subjects who meet the laboratory criteria for Hy's law will also be provided for Parts A and B combined. Two alternative definitions of criteria for Hy's law will be considered, defined as 1) (ALT or AST) >3 ×ULN, ALP \leq 2.0 ×ULN, and total bilirubin >1.5 ×ULN; and 2) (ALT or AST) >3 ×ULN, ALP \leq 2.0 ×ULN, and total bilirubin >2 ×ULN. Using a conservative approach for detecting any potential Hy's law cases, subjects meeting either criteria based on any combination of post-baseline laboratory results, irrespective of their temporal association, will be listed. All laboratory results for the parameters included in the criteria will be presented by visit for all subjects who meet the criteria.

Detailed patient listings of all laboratory data collected during the study will be provided. Laboratory values outside normal limits will be identified in the patient data listings. A column will display any applicable toxicity grading of the laboratory value.

